## 5. Outcomes

Primary outcome: Postoperative duration of drain placement (days)

Secondary outcomes: All outcomes are measured within 6 months of the initial surgery

- Episodes of seroma formation requiring aspiration

November 24, 2016

- Loss of implant
- Revisional surgery/ return to operating room
- Wound dehiscence or debridement
- Capsular contracture (as identified by the plastic surgeon)
- Number of additional postoperative clinic visits with the plastic surgeon (beyond the routine)
- Economic impact will be assessed based on calculation of total costs with each material used to include the material costs, duration of operative room use, clinic and inpatient hospital costs, surgical billing costs and anaesthesia costs

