## **6. Study Procedures**

All patients undergoing mastectomy for breast cancer or breast cancer prophylaxis are seen at the WBHC at the Ottawa Hospital. Patients eligible and consenting for immediate breast reconstruction with an implant will be introduced to the REACT-ADM study and a standardized verbal consent for randomization will be recorded in the clinic notes. The clinical research assistant (CRA) will be performing the randomization and will inform the surgeon on the day of surgery with regards to the randomization arm immediately before the surgery. Both Dermacell and AlloDerm will be readily available in the operating room for use in case of randomization into either arm.

The plastic surgeon will be informed of the randomization arm and will proceed with the surgery in the usual fashion, with standard, equivalent procedures used for both (aseptic technique, drainsplacement, oral antibiotics for 1 week postoperatively). The routine schedule of postoperative follow-up of these patients is as follows:

November 24, 2016

Breast Surgeon:

- 2 weeks
- 6 months

Plastic Surgeon:

- 1 weeks
- 2 weeks
- 6 months

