## **7. Sample size calculation and Data Analysis Plan**

The primary endpoint of the study is drain duration (days). Mean postoperative duration of drain placement is 10 days. As per informal discussion with the plastic and breast surgeons, a minimum of 4 days in drain duration between the 2 arms will be considered clinically significant. We are hypothesizing that there will be minimum of 4 day difference in drain duration, in favour of Dermacell as this is a superiority trial. As such, we will require 50 patients total (25 per arm) to demonstrate a 4 day difference in drainage duration (14 vs 10) with a standard deviation of 5. Allowing for a 10% study drop out rate, we will require a total of 56 pts or 28 patients per arm. The Ottawa Hospital currently performs 100 immediate breast reconstructions per year with ADM. As such, the study duration would be expected to be 1 years. Data will be analysed at the end of the year.

November 24, 2016

The primary endpoint of the study is drain duration (days). We will compare mean postoperative duration of drain placement between both arms by calculating the post-randomization absolute mean difference in durations and its 95% confidence interval. We will also present the associated two-sample t-statistic. If data are not normally distributed, we will compare groups using a Mann-Whitney test. Our dichotomous secondary outcomes (episodes of seroma formation requiring aspiration, loss of implant, revisional surgery/ return to operating room, wound dehiscence or debridement, capsular contracture (as identified by the plastic surgeon) will be analyzed by calculating relative risk ratios and their 95% confidence intervals. Our continuous outcome (number of additional postoperative clinic visits with the plastic surgeon beyond the routine) will be analyzed using parametric (t-statistic) or non-parametric (Mann-Whitney) tests depending on distribution of occurrences. Patients having bilateral mastectomy will have each breast evaluated separately, as 2 entries the final results database. Both breasts of the same patient will receive the same randomization arm.

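### The additional-visits outcome does not exclude drain-only visits, so it may partly repeat the primary outcome; it also has no planned estimate and no per-patient counting rule

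*Combined protocol and SAP*

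**What the plan says.** Section 5 names the primary outcome: "Primary outcome: Postoperative duration of drain placement (days". Among the secondary outcomes it lists "Number of additional postoperative clinic visits with the plastic surgeon (beyond the routine", and it fixes the window for these: "All outcomes are measured within 6 months of the initial surgery".

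The only definition of routine is in Section 6. After the words "The routine schedule of postoperative follow-up of these patients is as follows", it gives the plastic surgeon visits at 1 week, 2 weeks and 6 months, and the breast surgeon visits at 2 weeks and 6 months. Nothing is scheduled between week 2 and month 6.

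Section 7 plans the trial to "demonstrate a 4 day difference in drainage duration (14 vs 10) with a standard deviation of 5". It promises a mean difference with a 95% confidence interval for the primary outcome, and relative risks with intervals for the dichotomous outcomes. The visit count "will be analyzed using parametric (t-statistic) or non-parametric (Mann-Whitney) tests depending on distribution of occurrences", and no estimate is named. Section 7 also enters a bilateral patient in the database twice, once per breast.

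No section gives a reason-for-visit rule, a window around the routine visits or a criterion for drain removal. None says who removes drains or at which visit.

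**The concern.** Read literally, a plastic-surgeon visit in week 3 made only to take out a drain is outside the routine schedule and would count. If the planned difference in drain duration is real, one arm has more drains still in at the last early routine visit, and it could collect more additional visits for that reason alone. Because Section 2 states the aim as postsurgical complications, a difference in visits could be taken as separate support for the primary result when part of it is that result seen again. The surgeon knows the arm (Section 6), so any influence on removal timing could also pass into the visit count and into the clinic costs of the economic outcome.

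Two further gaps need no assumption about drain practice. A p-value does not say how many visits a product saves. And a clinic visit belongs to a patient, not a breast, so a database with two entries per bilateral patient could record one visit twice.

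**Working it through.** **1. The plan's own figure.** Inputs from Section 7: difference 4 days, SD 5. Alpha, sidedness and power are not stated; two-sided 5% and 80% are assumed. n per arm = 2 × (1.960 + 0.842)² × 5² / 4² = 2 × 7.85 × 25 / 16 = 24.5, rounded up to 25. With 10% dropout, 50 / 0.90 = 55.6, rounded up to 56. Both agree with Section 7 ("Allowing for a 10% study drop out rate, we will require a total of 56 pts or 28 patients per arm").

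**2. Drains still in after the 2-week visit.** Take that visit as day 14. For a normal distribution, P(duration > 14) = 1 − Φ((14 − mean) / 5).
- Mean 14: 1 − Φ(0) = 0.500
- Mean 10: 1 − Φ(0.8) = 0.212

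Durations may be skewed, so the same means and SD were also put into gamma and lognormal shapes:

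| Shape | Mean 14 | Mean 10 | Gap |
|---|---|---|---|
| Normal | 0.500 | 0.212 | 0.288 |
| Gamma | 0.452 | 0.191 | 0.262 |
| Lognormal | 0.431 | 0.171 | 0.260 |

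The gap also depends on the cut-off, because no visit window is given. With day 16 (assumed) and the normal shape it is (1 − Φ(0.4)) − (1 − Φ(1.2)) = 0.345 − 0.115 = 0.23.

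**3. From late drains to counted visits.** Let q be the share of late drains that cause one separate plastic-surgeon visit. The documents do not give q. The expected difference from drain duration alone is q × 0.288: 0.07 visits per patient at q = 0.25, 0.14 at q = 0.5 and 0.29 at q = 1.

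**4. Overlap with the primary outcome.** Let λ be the mean number of other additional visits per patient, equal in both arms; it is also not given. The drain-only share of all additional visits is q × 0.356 / (λ + q × 0.356), where 0.356 = (0.500 + 0.212) / 2. A simulation (2,000 trials per setting, 25 per arm, normal durations, Poisson other visits) gave the following. Each cell shows the Mann-Whitney rejection rate at two-sided 5%, the Spearman correlation with drain duration, and the drain-only share:

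| λ | q = 0.25 | q = 0.5 | q = 1 |
|---|---|---|---|
| 0 | 13%; 0.34; 100% | 28%; 0.51; 100% | 59%; 0.82; 100% |
| 0.25 | 7%; 0.17; 26% | 13%; 0.33; 42% | 34%; 0.60; 59% |
| 0.5 | 6%; 0.13; 15% | 10%; 0.25; 26% | 25%; 0.50; 42% |
| 1.0 | 5%; 0.10; 8% | 7%; 0.18; 15% | 15%; 0.38; 26% |

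With q = 0 and λ from 0.25 to 1.0 the rejection rate is about 5%.

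**5. Double entry.** A bilateral patient with one extra visit recorded under both breasts contributes two visits on two rows. Her visit total doubles, and a test on rows treats the pair as independent. The documents give neither the proportion of bilateral patients nor the row on which a visit is recorded, so this is not sized.

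**The case against.** A reader might infer three stronger things, and the documents support none of them.

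- *The plan counts drain-only visits.* It does not say so; it neither includes nor excludes them. Removal by the breast surgeon or other staff, or at a routine visit, would add nothing to the count.
- *The outcome largely re-measures drain duration.* On the planning figures 50% to 79% of patients have the drain out by day 14, and removal at the 1- or 2-week visit is not an additional visit. The correlation is high only if nearly all late drains need a separate visit and other extra visits are rare. At q = 0.25 it is 0.10 to 0.34.
- *The rejection rates are false positives against a nominal 5%.* They are not. In those simulations the mean number of visits truly differs, so they show power to detect a real difference in visits. If drain durations do not differ, this mechanism produces nothing.

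Two further objections also stand. Section 1.1 treats drain duration as a measure of seroma, so arms that differ by 4 days do not have identical complications in the protocol's own terms. The total visit count is also a legitimate measure of patient burden and resource use. Both are reasons to keep the total as the stated outcome and to make the split a supporting breakdown.

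The objection does not remove the ambiguity itself. Without a recorded reason for each visit, the trial cannot show which row and column of the table applies to it.

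**Conclusion.** The point holds in a limited form. The definition does not exclude drain-only visits and no routine plastic-surgeon visit falls between week 2 and month 6, so the outcome may partly repeat the primary one. The contribution is up to about 0.26 to 0.29 visits per patient. That ceiling assumes the planned 14 vs 10 days (SD 5), a week-2 visit on day 14 and one separate plastic-surgeon visit for every late drain. If a quarter of late drains need one, it is about 0.07. The missing estimate is plain from Section 7. The possible double count follows from its two-entries rule if visits are recorded per breast. This is a definition and reporting weakness in one secondary outcome. It does not undermine the primary analysis, and it is worth correcting because the correction is cheap.

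**What to change.** In Sections 5 and 7:
- Count additional plastic-surgeon visits once per patient, whatever the number of breasts reconstructed.
- Keep the total as the stated outcome and as the input to the economic analysis.
- Have the clinical research assistant code the reason for each additional visit from the dictated note, by a rule fixed before data collection. Report visits made only to check or remove a drain, and all other additional visits, as a supporting breakdown.
- For the total and each part, give the difference in mean visits per patient with a 95% confidence interval, alongside any test.

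The cost is one reason code on the data form and a few sentences. No patients, visits or staff are added, since Section 8 already has the assistant collecting data from records and dictated notes.

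There are three downsides. The assistant performs the randomization and the surgeon is told the arm, so the coding is not blinded. Some visits will have mixed reasons, so show the breakdown with these assigned each way. The non-drain count will have fewer events and a relatively wider interval.

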Various ADMs are offered on the market and the costs vary widely despite very similar qualities. The two most commonly used ADM products in North America by far are Dermacell and Alloderm [2-4,32]. The difference between the two products include a) the level of sterility , with Dermacell being sterilized to  $10^{-9}$  while Alloderm is sterilized to  $10^{-6}$  and b) the consistency and thickness of the biologic material and c) a significant difference in cost (standard 6x16cm piece of Dermacell = \$2200 CAD and Alloderm = \$3600 CAD). For a typical patient, the difference in cost for the hospital is about \$1400. Supporters of Dermacell advocate for its lower cost and increased sterility; whether the difference in sterility translates into a clinical difference in infection rate is unclear (standard procedure is to sterilize to  $10^{-6}$  for operative devices) [32-36]. Supporters of Alloderm advocate based on its longer term data on safety and effectiveness (2-4,19,32] as it is the ADM that has been around the longest. Each product has shown to be safe and effective (32-26). As such there exists clinical equipoise. Currently, the selection of ADM is based on non-clinical idiosyncratic decision making factors, such as the hospital's previous relationship with the vendors and preference of the surgeon. Both products are equally available to Canadian hospitals and currently at the Ottawa Hospital the product used is dependent on surgeon preference.

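### The economic outcome has no unit, between-arm contrast or interval: Section 5 plans only total costs for each material, and Section 7 does not analyse cost

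*Combined protocol and SAP*

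**What the plan says.** Section 5 (Outcomes) makes economic impact a secondary outcome and states its method: "Economic impact will be assessed based on calculation of total costs with each material used to include the material costs", continuing with "duration of operative room use, clinic and inpatient hospital costs, surgical billing costs and anaesthesia costs". All secondary outcomes run to 6 months after the initial surgery.

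Section 7 (Sample size calculation and Data Analysis Plan) gives drain duration a mean difference with a 95% CI and a t-statistic, or a Mann-Whitney test if the data are not normal. The five dichotomous outcomes get relative risks with 95% CIs. One further outcome is covered: "Our continuous outcome (number of additional postoperative clinic visits with the plastic surgeon beyond the routine) will be analyzed using parametric" or non-parametric tests. Cost does not appear.

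The Study Design section randomises the patient, with both breasts of a bilateral case in the same arm. It also enters the two breasts as separate records in the results database, as do Sections 7 and 8. No section says which unit applies to cost.

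Section 1 (Background) prices one standard piece at $2200 CAD for Dermacell and $3600 CAD for Alloderm. It adds: "For a typical patient, the difference in cost for the hospital is about" $1400.

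**The concern.** A cost comparison needs a unit, a contrast and a measure of uncertainty. The plan supplies a list of components and the word total.

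- **Unit.** With two records for a bilateral patient, costs shared by one operation, such as theatre time and anaesthesia, could be split between records, counted twice or assigned to the patient. The plan does not choose.
- **Contrast.** A total for each material grows with the number of patients in that arm and the number of breasts reconstructed. It is not an effect estimate.
- **Uncertainty.** Two totals from a trial of 56 patients do not show how far chance could account for their difference.

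Price is one of the three differences between the products that Section 1 names, and lower price is an argument it reports for Dermacell. Readers will therefore look at the cost result, and without an interval they cannot tell a real difference from noise.

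**Working it through.** **1. The plan's own figures.** The cost outcome has no sample size or precision figure, so the number available comes from the primary outcome. Section 7 sizes the trial "to demonstrate a 4 day difference in drainage duration (14 vs 10) with a standard deviation of 5". It states no alpha or power; two-sided 5% and 80% are assumed here.

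- n per arm = 2 × (1.960 + 0.842)² × 5² / 4² = 24.5, rounded up to 25. This matches the plan.
- Dropout: 50 / 0.90 = 55.6, so 56 in total and 28 per arm. This matches.
- Price gap: 3600 − 2200 = $1,400 for one piece. This matches.

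**2. Which outcomes have an analysis.** Setting the Section 5 list against Section 7:

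| Outcome | Analysis in Section 7 |
|---|---|
| Drain duration | Mean difference, 95% CI, t or Mann-Whitney |
| Seroma aspiration, implant loss, revision, dehiscence or debridement, contracture | Relative risk, 95% CI |
| Additional clinic visits | t or Mann-Whitney |
| Economic impact | None |

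Section 7 refers to a single continuous outcome and identifies it as visits, so cost is not covered by implication.

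**3. Totals depend on arm size.** On material cost alone, at one piece per patient (an assumption):

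- 28 v 28: Dermacell 28 × 2200 = $61,600; Alloderm 28 × 3600 = $100,800.
- 35 v 21: Dermacell 35 × 2200 = $77,000; Alloderm 21 × 3600 = $75,600.

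The second pair has the opposite order although the price per piece is unchanged. No blocking is stated. Under simple randomisation (assumed), 35 or more of 56 patients would receive Dermacell with probability about 4%. A mean per patient does not have this problem.

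**4. The answer depends on the unit.** The series in Table 1 add up to 1136 breasts in 678 patients, or 1.68 breasts per patient. If each breast takes one piece (an assumption; the documents do not say), the material gap is $1,400 per breast record and 1136/678 × 1400 = about $2,346 per patient at that mix. The local mix is not given. The example shows only that the unit has to be fixed in advance.

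**5. Precision of a per-patient mean difference.** The documents give no cost SD, so a range is shown. SE = SD × √(2/n). Half-width = t(0.975, 2n − 2) × SE, with t = 2.005 at n = 28 and 2.011 at n = 25.

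| Assumed SD | SE, 28 per arm | Half-width, 28 per arm | Half-width, 25 per arm |
|---|---|---|---|
| $1,000 | $267 | $536 | $569 |
| $2,000 | $535 | $1,072 | $1,137 |
| $3,000 | $802 | $1,607 | $1,706 |
| $5,000 | $1,336 | $2,679 | $2,843 |
| $10,000 | $2,673 | $5,358 | $5,687 |

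The half-width equals $1,400 at SD = 1400 / (2.005 × √(2/28)) = about $2,610 with 28 per arm, and at about $2,460 with 25 per arm. Below that SD the interval is narrower than the one-piece gap on each side; above it, wider.

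**The case against.** The strongest reply is that a sensible per-arm comparison is probably intended. Total can mean the sum of the cost components for a patient, not the sum over an arm. Each material can mean each arm. Cost is a secondary outcome with no decision rule, and the aim and hypothesis concern complications. This reply stands as a reading of intent and limits the importance of the point. It does not supply the unit, the contrast or the interval, which are missing on any reading.

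The consequence also depends on an SD nobody has stated. At $1,000 to $2,000 the interval is narrower than the $1,400 gap. If the true gap were $2,346 per patient, the half-width would exceed it only above an SD of about 2346 / 0.536 = $4,380. This stands too, so no claim is made here that the comparison will be uninformative.

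A reader might infer four stronger points that the documents do not support:

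- **That randomisation is given up by grouping on the material used.** Section 6 keeps both products in theatre so that either allocation can be carried out, and nothing anticipates crossover. The wording is loose, but that does not show randomisation is abandoned.
- **That case mix would reverse the price gap.** Take 28 per arm, an assumed bilateral share p of 40% to 68%, and $2,900 per extra piece (the mean of the two prices). Chance imbalance then moves the per-patient material difference with an SD of √(2p(1 − p)/28) × 2900, about $360 to $390. A shift of $1,400 is more than 3.6 of these SDs. Reversal becomes appreciable only with large other costs per breast, which the documents do not give.
- **That an interval would correct a result favouring the wrong product.** It displays chance error and leaves the sign of the estimate unchanged.
- **That $1,400 in Section 1 must be restated per breast.** This assumes one piece per breast, which is not stated, and concerns background text.

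**Conclusion.** The point holds as a gap in the specification of a secondary outcome. Cost is the only outcome listed in Section 5 without an analysis in Section 7. The method that is stated yields totals with no defined unit, a dependence on arm size and number of breasts, and no uncertainty. These faults rest on the text alone and need no assumption about cost.

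The size of the consequence is not known. At 28 per arm the half-width runs from about $540 (SD $1,000) to about $2,680 (SD $5,000) and passes the one-piece price gap at an SD of about $2,600. All the SDs are assumed, and the t-based half-widths ignore the skew that cost data usually show. Whether the trial can say anything useful about cost will be seen only if an interval is reported. The change should be made, but the primary comparison is unaffected.

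**What to change.** In Sections 5 and 7:

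- Define the outcome as total cost per randomised patient to 6 months, summed over the components already listed, with one cost record per patient whether one or two breasts are reconstructed.
- Compare by randomised arm, as the difference in mean cost with a 95% CI from a bootstrap that resamples patients. The bootstrap allows for skew and keeps the mean, which is the quantity a budget needs.
- Adjust for the number of breasts reconstructed (1 or 2). This is already recorded and affects material, theatre and billing costs.
- Optionally, report the difference with and without the ADM price, to separate the known price gap from costs that arise from care.

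The cost of the change is a few lines of plan text and a little more analysis, with no new data and no change to patient care. The resulting cost statement will look less certain than two bare totals, because its uncertainty is shown.

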## **6. Study Procedures**

All patients undergoing mastectomy for breast cancer or breast cancer prophylaxis are seen at the WBHC at the Ottawa Hospital. Patients eligible and consenting for immediate breast reconstruction with an implant will be introduced to the REACT-ADM study and a standardized verbal consent for randomization will be recorded in the clinic notes. The clinical research assistant (CRA) will be performing the randomization and will inform the surgeon on the day of surgery with regards to the randomization arm immediately before the surgery. Both Dermacell and AlloDerm will be readily available in the operating room for use in case of randomization into either arm.

The plastic surgeon will be informed of the randomization arm and will proceed with the surgery in the usual fashion, with standard, equivalent procedures used for both (aseptic technique, drainsplacement, oral antibiotics for 1 week postoperatively). The routine schedule of postoperative follow-up of these patients is as follows:

November 24, 2016

Breast Surgeon:

- 2 weeks
- 6 months

Plastic Surgeon:

- 1 weeks
- 2 weeks
- 6 months

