but also enabling major national and international initiatives to generate the data needed to improve care. As such, the Integrated Consent Model is being increasingly used internationally to improve patient care. In fact, the Ottawa Hospital Cancer Centre is leading this program with over 150 patients already enrolled on REACT trials at four Canadian Cancer Centres (Ottawa, Kingston, Edmonton, Kitchener). These studies have shown excellent patient feedback with 97% of patients rating being ‘completely satisfied’ with the REACT process.

Thus, we propose a pragmatic clinical trial to evaluate AlloDerm with Dermacell in a head to head randomized fashion, with regards to the postoperative complications, namely infection, seroma formation (as measure by drain duration and output), loss of the implant, incidence of revisional surgery and capsular contracture. These postoperative sequelae have significant implications to the patient, surgeon and health care system. The most significant of these are postoperative infection, which can result in prolonged antibiotic use, hospital admission, loss of implant, and delay in adjuvant breast cancer therapy.

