### **3. Hypothesis**

We predict that Dermacell will have reduced postoperative complications as compared to Alloderm due to its improved sterility.

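### Drain duration ends at a removal decision, but the plan sets no common removal criterion and names no decider while the plastic surgeon knows the arm, so the primary comparison is open to bias of unknown size and direction.

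*Combined protocol and SAP*

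**What the plan says.** Section 5 defines the endpoint in one line: "Primary outcome: Postoperative duration of drain placement (days"). Section 7 repeats it and adds no end event, removal rule or decision-maker.

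On knowledge of the arm, Section 6 says that the research assistant "will inform the surgeon on the day of surgery with regards to the randomization arm immediately before the surgery", and then: "The plastic surgeon will be informed of the randomization arm and will proceed with the surgery in the usual fashion". The procedures to be held equal are "standard, equivalent procedures used for both (aseptic technique, drainsplacement, oral antibiotics for 1 week postoperatively"). Putting the drain in is on that list; taking it out is not. The routine schedule in Section 6 has the plastic surgeon seeing patients at 1 week, 2 weeks and 6 months, and the breast surgeon at 2 weeks and 6 months.

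Drain output appears only in Section 1.1, as part of "seroma formation (as measure by drain duration and output"). It is neither an outcome in Section 5 nor a trigger for removal.

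The expected direction is stated twice. Section 3: "We predict that Dermacell will have reduced postoperative complications as compared to Alloderm due to its improved sterility". Section 7, on the primary endpoint itself: "We are hypothesizing that there will be minimum of 4 day difference in drain duration, in favour of Dermacell". Section 1 describes supporters of each product and notes that "currently at the Ottawa Hospital the product used is dependent on surgeon preference".

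Under Section 8 the research assistant, who in Section 6 also performs the randomization, takes the data from health records and dictated surgeon notes. No assessor unaware of the arm is mentioned.

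**The concern.** Drain duration is not an instrument reading. It ends at a clinical decision, and two clinicians looking at the same patient may reasonably choose different days. If the decider knows the arm and has a view about the products, and no shared rule limits the choice, the removal date can carry that view into the data.

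Randomization balances patients at baseline but not a decision taken afterwards with the arm known. The planned t-test or Mann-Whitney test takes the recorded durations as given. A larger sample would only estimate the biased difference more precisely. Adjusting for surgeon would not remove it either, because the bias acts between arms within a surgeon.

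At stake is the interpretation of the only primary comparison. A difference for Dermacell might partly reflect earlier removal in the favoured arm, and a preference for AlloDerm could hide a real difference.

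**Working it through.** **Inputs.** From Section 7: difference 4 days (14 vs 10), SD 5, 25 per arm, 28 per arm after 10% dropout, and a 95% confidence interval with a two-sample t-statistic. Section 7 states neither alpha nor power for the sample size. I assume two-sided 5%, in line with the 95% interval, and 80% power. The size of any shift in removal timing is also assumed, because the documents give none.

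**1. The plan's sample size reproduces.**
n per arm = 2 × (1.960 + 0.842)² × 5² / 4² = 24.5, rounded up to 25, so 50 in total. With 10% dropout, 50 / 0.9 = 55.6, so 56. Two-sided 90% power would need 33 per arm, one-sided 80% would need 20 and one-sided 90% would need 27, so only two-sided 5% with 80% power gives 25. The sample-size arithmetic is not at fault.

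**2. Smallest significant difference.**
SE = 5 × √(2/25) = 1.414 days. The critical difference is t(0.975, 48 df) × 1.414 = 2.84 days.

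**3. No true effect, but a net shift b in removal timing towards Dermacell.**
The chance of a significant result favouring Dermacell comes from the noncentral t distribution with 48 df and noncentrality b / 1.414:

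| Assumed shift b (days) | Chance of significance favouring Dermacell |
|---|---|
| 0 | 2.5% |
| 0.5 | 5.3% |
| 1 | 10.3% |
| 1.5 | 17.9% |
| 2 | 28.3% |

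At 28 per arm, with no dropout, the 1-day and 2-day figures are 11.0% and 31.2%.

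**4. A shift the other way.**
If a true 4-day advantage is observed as 3 or 2 days because removal timing favours AlloDerm, exact t-test power at 25 per arm falls from 79% to 55% or 28%.

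**5. Reaching the plan's own 4-day margin.**
With no true effect, the chance of an observed difference of at least 4 days is 1 − Φ((4 − b) / 1.414). This is 0.2% at b = 0, 1.7% at b = 1 and 7.9% at b = 2.

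These figures treat patients as independent. Entering both breasts of a bilateral patient as separate records is a separate matter.

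**The case against.** Several points on the other side have force.

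- **The decider is not named.** A reader might infer that the plan gives the removal decision to the plastic surgeon. It does not say so. The inference rests on the week 1 and week 2 visits, and the breast surgeon also sees patients at 2 weeks. This narrows the statement but does not remove the gap: whoever decides, there is no criterion and no provision for that person to be unaware of the arm.
- **Removal need not follow the visit schedule.** Because the early visits are 7 days apart, a reader might reason that moving removal one visit earlier in 2 of 7 patients shifts the mean by 2 days. The documents do not support this. If drains came out only on days 7 and 14, a mean of 10 would need 3/7 of removals on day 14, giving SD = 7 × √(3/7 × 4/7) = 3.46, and no mix could exceed 3.5. The plan uses SD 5, and Section 5 counts clinic visits beyond the routine ones. The shifts used above therefore remain bare assumptions.
- **Direction is not settled.** The protocol expects Dermacell to do better, but Section 1 describes equipoise and supporters of both products. Opposing preferences could partly cancel, and the documents give no balance of preferences. This stands.
- **The trial is pragmatic.** It compares two standard-care products that differ in consistency and thickness, so masking the operating surgeon is not realistic. This stands too, but a shared removal criterion does not require it.
- **The 2-day case is severe.** It is half of the difference the plan regards as clinically important. At 0.5 day the effect on the error rate is small, and few null trials would show the full 4 days.

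**Conclusion.** The point holds in a limited form. The primary endpoint ends at a discretionary decision with no common criterion and no named decider, in a trial where the plastic surgeon knows the arm and the protocol states which arm should win. Followed as written, the plan leaves the comparison open to bias of unknown size and either direction, which neither randomization nor the planned tests can remove.

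The size can only be illustrated. Against a nominal 2.5%, assumed net shifts of 0.5, 1 and 2 days towards Dermacell give about 5%, 10% and 28%. These figures rest on 25 per arm, SD 5, a two-sided 5% test and no true effect.

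A reader might go further and infer that a positive result could not be attributed to the matrix at all. The documents do not support that, because nothing in them shows that a shift would occur or how large it would be. I class this as something the sponsor should fix, not as a defect that invalidates the design.

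**What to change.** In Sections 5 and 6:

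1. Before the first patient, the participating surgeons agree one drain-removal criterion drawn from their existing practice and apply it identically in both arms. No value is proposed here; that is a clinical choice for them.
2. State who judges whether the criterion is met.
3. For each drain, record on the CRF the date the criterion was met and the date the drain was actually removed.
4. Keep actual drain duration as the primary endpoint, so that the planning mean and SD in Section 7 still apply. Report time to criterion as a supporting analysis. A difference between arms in the gap between the two dates would point to removal timing that the criterion does not explain.
5. Optionally, where existing staff allow, have the criterion judged by someone not told the arm, and leave the arm off drain instructions and clinic sheets. This should not be mandatory: the plan identifies no such person, and if the operating surgeon also runs the early visits, masking could need additional staff.

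The cost is protocol wording, one agreed criterion and two CRF dates per drain. Surgeons give up some discretion over removal. Any masking will be imperfect, for example if the operative note is open to the person judging. The criterion must be fixed before enrolment, because no later analysis can supply it.
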